4.6.2.2 Adverse Events during the OOE

Adverse events during the OOE will be handled and reported using the same general approaches as described above for the ISP.

An adverse event profile summary table will be presented to provide an overview of adverse events reported in the OOE. Adverse events and serious adverse events will be summarized by SOC and PT also.

Concomitant treatments for adverse events will be summarized by class and PT. Also concomitant treatments starting during the OOE or during the SFU Period following the OOE will be summarized by class and PT.

The number of patients who experienced an adverse event within the OOE that led to interruption of study drug will be summarized by SOC and PT for each treatment group.

4.6.2.3 Adverse Events, All Study Periods

When presenting adverse events across all study periods, the same general approaches to handling and reporting adverse events will be applied, as described above for the ISP.

Ocrelizumab—F. Hoffmann-La Roche Ltd
27/Statistical Analysis Plan BN29739

An adverse event profile summary table will be presented to provide an overview of adverse events reported in the OOE. Adverse events and serious adverse events will be summarized by SOC and PT also.

Concomitant treatments for adverse events (excluding IRRs and MS relapses) will be summarized by class and PT.

Concomitant procedures/surgeries will be summarized by class and PT.

4.6.3 Selected Adverse Events

4.6.3.1 Progressive Multifocal Leukoencephalopathy

PML will be categorized as a serious adverse event per guidance on the diagnosis of PML in protocol. Patients with PML, if any, will be included in the listing of serious adverse events.

4.6.3.2 Infections and Serious Infections

Infections will be defined from the adverse event data using the MedDRA SOC of “Infections and Infestations”. An infection will be defined as serious if the event is a serious adverse event.

A listing of infections (defined using the MedDRA SOC “Infections and Infestations”) with pathogen information code will be provided. An additional listing will display adverse events from other SOCs with the pathogen information code. Also a listing will display non-serious infections treated with an intravenous anti-infective.

Immunization Study Period

Infections and serious infections will be summarized by SOC and PT. Infections by intensity will be summarized also. If a patient has multiple events, the most extreme intensity will be taken. Infections and serious infections will also be summarized by pathogen type. The number of infections and serious infections per 100 patient-years will be calculated and summarized.

Optional Ocrelizumab Extension

The same summaries will be presented for OOE as for ISP, with the exception of summaries of infections and serious infections by pathogen type.

All Periods

The same summaries will be presented for all study periods as for ISP.

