Approximately 30–35 centers will participate in the study in the United States/North America. This study consists of up to five study periods:

- Screening Period
- Immunization Study Period

Group A: Immunization Study Period and OCR treatment starts at Day 1/Week 1. Patients will receive 300 mg of open-label OCR on Day/Week 1 (Dose 1 Infusion 1) and Day 15/Week 2 (Dose 1 Infusion 2). Patients in Group A will be split and be assigned to either Group A1 (booster 13-PCV) or Group A2 (influenza vaccine). At Day 85/Week 12 patients will start to receive immunizations and undergo post-immunization assessments. For all patients in Group A, the Immunization Study Period will end on Day 169/Week 24.

Group B: Patients will not receive OCR. At Day 1/Week 1, patients will start to receive immunizations and undergo post-immunization assessments. For Group B, the Immunization Study Period will end at Day 84/Week 12.

The timing of immunizations and post-baseline assessments are detailed in [Appendix 1](#).

[figure not shown]
- Optional OCR Extension (OOE) Period:
 - **Groups A1 and A2:** Patients who complete the 24-week immunization study period will have the option for retreatment with a single infusion of 600 mg OCR (Dose 2) at Day 169/Week 24 and subsequent single infusions (600 mg OCR) at intervals of 24 weeks provided that he or she meets the OOE retreatment criteria and chooses to receive retreatment.
 - **Group B:** Patients who complete the 12-week immunization study period will have the option to receive OCR in the OOE; the first dose will be administered as two single infusions of 300 mg, on Day 84/Week 12 (Dose 1 Infusion 1) and Day 98/Week 14 (Dose 1 Infusion 2), and subsequent doses will be administered as single 600 mg infusions (Dose 2, Dose 3, etc.) at intervals of 24 weeks provided that he or she meets the OOE retreatment criteria and chooses to receive retreatment. Group B patients who do not qualify for and/or do not choose treatment with OCR at Week 12 will complete the study at Week 12 and will **not** enter safety follow-up.

Please note that the OOE will continue with all patients who are able to receive OCR as per local guidelines, or unless the Sponsor decides to terminate the OCR program for MS; however, the OOE will not exceed 4 years after the last patient last visit in the Immunization Study Period. *At the end of the OOE, patients may choose to continue on commercially available OCR.*

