6.5 SAFETY ANALYSES

All subjects who received any amount of OCR or any vaccine will be included in the safety analyses and will be analyzed according to the treatment received.

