4. STATISTICAL METHODS

Except where stated otherwise, all tabular and graphical summaries of data, which are presented by treatment group, will separately show results from the following four groups:

- Group A1 (ocrelizumab + 13-PCV vaccine)
- Group A2 (ocrelizumab + influenza vaccine)
- Group A overall (Groups A1 + A2)
- Group B (control)

All listings will show study data for each treatment group in the order shown above.

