4.6 SAFETY ANALYSES

For safety analyses, data will be presented for Groups A1 and A2 separately as well as for Group A (Groups A1 and A2 combined) and B.

All summaries of safety data will be based on the Safety Population.

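### The all-study-periods adverse event and infection tables mix Group B's time off and on ocrelizumab in one column, and no table in the SAP shows all ocrelizumab-exposed time together

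*SAP*

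**What the plan says.** SAP section 4 sets the default layout: "all tabular and graphical summaries of data, which are presented by treatment group, will separately show results from the following four groups". The groups are A1, A2, A overall, and a fourth given as "Group B (control"). SAP 4.6 repeats these columns for safety: "data will be presented for Groups A1 and A2 separately as well as for Group A (Groups A1 and A2 combined) and B".

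For the immunization study period (ISP), SAP 4.6.3.2 plans infections by term, intensity and pathogen type, and adds: "The number of infections and serious infections per 100 patient-years will be calculated and summarized". The optional ocrelizumab extension (OOE) gets the same set without the pathogen-type summaries. For all periods: "The same summaries will be presented for all study periods as for ISP". SAP 4.6.2.3 says of adverse events: "When presenting adverse events across all study periods, the same general approaches to handling and reporting adverse events will be applied".

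Protocol 3.1 says of Group B: "Patients who complete the 12-week immunization study period will have the option to receive OCR in the OOE". The first infusion is scheduled at Week 12.

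Protocol 6.5 says that patients given any ocrelizumab or vaccine "will be included in the safety analyses and will be analyzed according to the treatment received". Protocol 6.5.1 then tabulates adverse events by Groups A and B. SAP 4.1.3 applies the treatment-received rule to patients given a wrong medication or vaccine.

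**The concern.** Group A is on or after ocrelizumab from Day 1. Group B is not: its treatment changes when it enters the OOE. Neither all-periods section splits Group B at its first infusion. The treatment-emergent window in SAP 4.6.2.1 opens at the first ocrelizumab dose or any vaccination, which is Day 1 for Group B, and it is not reset later. Group B's all-periods counts and patient-years therefore join two exposure states in proportions set by OOE uptake and length of follow-up.

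The safety objective (Protocol 2.3) is to collect more data on the safety of ocrelizumab. A reader who takes the Group B column as a control rate, or as an on-drug rate, would be wrong both ways. A reader who sets it beside Group A sees a contrast pulled toward 1.

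**Working it through.** The documents state no figure for this point, so there is none to reproduce. They also give no event rates for this trial, no OOE uptake, and no follow-up at the clinical cutoff. The arithmetic below shows scale only.

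**Inputs from the documents**
- About 100 patients at 2:1 (Protocol 6.1), so about 33 in Group B.
- Group B's ISP ends at Day 84/Week 12 (Protocol 3.1). The first infusion may be later if influenza vaccination is late (Protocol 4.4.2.5).
- Only OOE and follow-up data available at the cutoff are analyzed (SAP 1).

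**Assumed inputs**
- OOE uptake u of 100% or 50%.
- Mean OOE time w of 12, 24, 48 or 96 weeks among entrants. When the last Group A patient reaches Week 24, a Group B patient randomized the same day is 12 weeks past the end of the ISP, so 12 is a natural low value.
- True ocrelizumab-to-control rate ratio R of 1.5, 2.0 or 0.5, with constant rates.

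**Step 1: off-drug share of the Group B column**

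Off-drug time = 33 × 12 weeks = 396 patient-weeks; 396 × 7 / 365.25 = 7.6 patient-years. Off-drug share s = 12 / (12 + u × w).

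| Mean OOE weeks | 12 | 24 | 48 | 96 |
|---|---|---|---|---|
| On-drug patient-years, u = 100% | 7.6 | 15.2 | 30.4 | 60.7 |
| s, u = 100% | 50% | 33% | 20% | 11% |
| s, u = 50% | 67% | 50% | 33% | 20% |

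With no OOE time, s is 100% and the problem vanishes.

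**Step 2: what the column and the A:B ratio would show**

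Pooled Group B rate relative to the control rate = s + (1 − s) × R. Apparent A:B ratio = R / [s + (1 − s) × R]. For R = 1.5, u = 100%, w = 12: pooled = 0.5 + 0.5 × 1.5 = 1.25, and 1.5 / 1.25 = 1.20.

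| Apparent A:B ratio, u = 100% | 12 wk | 24 wk | 48 wk | 96 wk |
|---|---|---|---|---|
| True R = 1.5 | 1.20 | 1.13 | 1.07 | 1.04 |
| True R = 2.0 | 1.33 | 1.20 | 1.11 | 1.06 |
| True R = 0.5 | 0.67 | 0.75 | 0.83 | 0.90 |

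At R = 1.5 the pooled Group B rate is 1.25, 1.33, 1.40 and 1.44 times the control rate across the row. At 12 weeks it is therefore 25% above the off-drug rate and 17% below the on-drug rate (1 − 1.25/1.5).

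R below 1 is included because Protocol 5.1.1.2 calls infection an identified risk but reports serious infections in the relapsing trials at 1.3% on ocrelizumab against 2.9% on interferon beta-1a, and Group B may stay on interferon beta.

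**Step 3: can the other planned tables replace the mixed column?**
- *Adverse event incidence:* no. SAP 4.6.2.1 counts patients with at least one event. A Group A patient with the same event in both periods appears in both tables, so the ISP and OOE counts cannot be added. Group A's all-periods count can be added to Group B's OOE count, but only by hand.
- *Infections by pathogen type:* no. The OOE set drops them, so Group B's on-drug summary exists only inside the mixed column. A patient listing with pathogen codes is planned, but it is not a summary.
- *Infections per 100 patient-years:* in part. Group A all-periods plus Group B OOE would give the all-ocrelizumab rate if counts and patient-years are both printed. But the OOE observation formula in SAP 4.6.1.2 runs from a dose given during the ISP, and Group B receives none, so Group B's start date is undefined.

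**The case against.** The strongest case against is that this is a labelling matter. The ISP table gives Group B off ocrelizumab and the OOE table gives Group B on it. The SAP plans no difference, ratio or interval for adverse events or infections, so no planned estimate is diluted. A cumulative table by randomized arm is a legitimate complete inventory, and starting Group B at its first infusion would delete its ISP events and drop patients who never enter the OOE. The SAP also leaves analyses of all patients given ocrelizumab to pooled programme analyses described elsewhere.

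Much of this stands. The harm is confined to the all-periods tables, and the by-arm inventory should be kept. It does not dispose of the point. The pathogen-type gap and the undefined Group B start date remain, this SAP describes no table of all ocrelizumab-exposed experience in this trial, and the pooled analyses are worded only as possible.

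A reader might infer two stronger things:
- *That the SAP breaches Protocol 6.5.* Protocol 6.5.1 itself tabulates by Groups A and B, and SAP 4.1.3 reads the rule as covering wrongly treated patients, which planned OOE dosing is not. This is an unresolved tension.
- *That every safety table will be headed control.* That word is in the default list in SAP 4. SAP 4.6 names Group B without it, so the printed header is likely but not certain.

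**Conclusion.** The point holds for the all-periods infection tables and for the adverse event tables by organ class and preferred term in SAP 4.6.2.3. The adverse event profile table in that section is worded as covering the OOE, so its scope is unclear. Once any Group B patient has OOE time at the cutoff and the two rates differ, the Group B column equals neither rate.

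The size is conditional. With full uptake and a true ratio of 1.5, the A:B ratio would read 1.20 to 1.04 over 12 to 96 mean OOE weeks; with lower uptake the distortion is smaller. Uptake, follow-up and the ratio are all assumptions.

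Two further readings go too far. The documents do not support saying that the column always understates the on-drug rate: for serious infections the direction could reverse. Nor are the first 12 weeks untreated: they are weeks without ocrelizumab, in which interferon beta may continue and study vaccines are given. The randomized ISP comparison and the primary endpoint are unaffected.

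**What to change.** In SAP 4.6.2.3 and the all-periods part of 4.6.3.2:
- Add a column *All ocrelizumab-exposed*: Group A from Day 1 plus Group B from its first ocrelizumab infusion, with matching patient-years and including infections by pathogen type.
- Define Group B's ocrelizumab start date for that denominator, and correct the formula in 4.6.1.2, which starts from an ISP dose that Group B never has.
- Keep the by-arm all-periods column as the complete inventory, but label it *Group B (control, then optional ocrelizumab)*. Drop *control* from OOE tables.
- State whether the adverse event profile table in 4.6.2.3 covers the OOE or all periods.
- Add a sentence saying how the treatment-received rule in Protocol 6.5 applies to Group B once it enters the OOE.

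The cost is SAP wording, one derived start-date variable from infusion dates already collected, and one extra column. The ISP tables do not change.

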4.6.3.3 Infusion-Related Reactions

An IRR and its corresponding symptoms are collected on the dedicated eCRF.

The symptom(s) of an IRR and the IRR itself may be of different intensities. As other symptoms can be recorded as free-text on the eCRF page, symptoms will be coded in

MedDRA and summarized by PTs. IRRs are categorized by the time of the event occurring during the infusion and within 24 hours of completion of the infusion.

A listing of patients with at least one IRR will be presented, including associated symptoms. This listing will be repeated to show the subset of patients with at least one IRR/symptom at Grade 3 or above (intensity).

Immunization Study Period

During the ISP, pretreatments will be summarized by infusion and overall, by class and PT (multiple occurrences of the same treatment in one individual are counted once per infusion).

By infusion and overall during the ISP, the number and percentage of patients with at least one IRR will be presented (patients with multiple events within an infusion will count only once). In addition, the total number of patients with IRR symptoms will be summarized by infusion and overall (multiple occurrences of an IRR symptom in one patient at one infusion (or overall) are counted once for that infusion (or overall)). The total number of IRR symptoms will also be summarized by infusion and overall. IRR symptoms will be summarized by SOC and PT.

During the ISP, the number and percentage of patients with IRRs and the total number of IRRs will be summarized by intensity and overall, and by infusion. For patients who have multiple IRRs, the most extreme intensity will be taken.

By infusion and overall during the ISP, the number and percentage of patients with at least one serious IRR will be presented (patients with multiple events within an infusion will count only once). In addition, the total number of patients with IRR symptoms resulting from serious IRRs will be summarized by infusion and overall (multiple occurrences of a serious IRR symptom in one patient at one infusion (or overall) are counted once for that infusion (or overall)). The total number of IRR symptoms resulting from serious IRRs will also be summarized by infusion and overall. Serious IRR symptoms will be summarized by SOC and PT.

By infusion and overall during the ISP, the number and percentage of patients with at least one IRR, the total number of IRRs, and the number of IRRs will be summarized by the time of events (during infusion, within 24 hours after end of infusion). Multiple occurrences of an IRR in one patient within one time period are counted once.

During the ISP, the number and percentage of patients reporting adverse events on the day or the day after an infusion, and the total number of such events will be presented, and these adverse events will be summarized by SOC and PT.

During the ISP, the number and percentage of patients receiving concomitant treatments for IRRs and the total number of such treatments will be presented, and these

concomitant treatments will be summarized by class and PT (multiple occurrences of the same treatment in one individual are counted once).

IRRs, serious IRRs and symptoms at Day 1, Dose 1 will be summarized separately for the 2 different ocrelizumab formulations used in this study (v0.4 and v1.0).

Optional Ocrelizumab Extension

By infusion and overall during the OOE, the number and percentage of patients with at least one IRR will be presented (patients with multiple events within an infusion will count only once). In addition, the total number of patients with IRR symptoms will be summarized by infusion and overall (multiple occurrences of an IRR symptom in one patient at one infusion (or overall) are counted once for that infusion (or overall)). The total number of IRR symptoms will also be summarized by infusion and overall. IRR symptoms will be summarized by SOC and PT.

During the OOE, the number and percentage of patients with IRRs and the total number of IRRs will be summarized by intensity and overall, and by infusion. For patients who have multiple IRRs, the most extreme intensity will be taken.

By infusion and overall during the OOE, the number and percentage of patients with at least one serious IRR will be presented (patients with multiple events within an infusion will count only once). In addition, the total number of patients with IRR symptoms resulting from serious IRRs will be summarized by infusion and overall (multiple occurrences of a serious IRR symptom in one patient at one infusion (or overall) are counted once for that infusion (or overall)). The total number of IRR symptoms resulting from serious IRRs will also be summarized by infusion and overall. Serious IRR symptoms will be summarized by SOC and PT.

4.6.3.4 Malignancies and Premalignant Lesions

Malignancies and premalignant lesions will be listed.

4.6.4 Laboratory Data

4.6.4.1 General Laboratory Evaluation

The summaries described below for general laboratory assessments will be produced for both the ISP and for the OOE separately.

For each laboratory test, absolute and changes from baseline values at each visit will be summarized by treatment group. Summary statistics calculated will include mean, median, SD, minimum, and maximum. The baseline value will be the last value prior to the first dose of ocrelizumab for patients in Group A and prior to the first immunization for patients in Group B. When laboratory data are presented over time, the laboratory values will be time-windowed into a common visit structure. If multiple values of the same laboratory parameter occur within the same time window, the worst value (i.e., the

value furthest away from the midpoint of the normal range) will be included in calculations of summary statistics.

For each laboratory test, the number and percentage of patients with single and replicated laboratory abnormalities will be summarized by treatment group.

In addition, for liver laboratory parameters, the number and percentage of patients with an elevated postbaseline AST or ALT levels will be summarized by treatment group.

During the SFU Period after either the ISP or the OOE, for each laboratory test, absolute and changes from baseline values at each visit will be summarized by treatment group. Summary statistics calculated will include mean, median, SD, minimum, and maximum. These summaries will only be presented if there is a sufficient volume of patient data available to allow meaningful interpretation.

Section 6.5.2 of the protocol states that for each laboratory test, individual patient values will be listed, and values outside the standard reference range will be flagged. To maintain consistency with the other Phase 3 studies in the ocrelizumab program, this data listing will not be prepared. The summary tables described above are considered adequate to describe general laboratory abnormalities, without the need for this data listing.

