4.5 IMMUNOPHENOTYPING ANALYSES

For immunophenotyping analyses, data will be presented for Groups A1 and A2 separately as well as for Group A (Groups A1 and A2 combined) and Group B.

Summaries will be presented separately within the following study periods:

- ISP
- SFU Period after the ISP (these patients did not enter the OOE)
- OOE
- SFU Period after completing the OOE

The humoral and cellular immunity outcome measures in this study are as follows:

- Flow cytometry, which will include (but is not limited to) the following cells:
 - Total B cells (CD19+)
 - B-cell subsets (e.g., memory B cells, naïve B cells, and plasma cells)
 - Total T cells (CD3+)
 - T helper cells (CD3+ and CD4+)
 - Cytotoxic lymphocyte T (CD3+ and CD8+)
 - Natural killer cells (CD3– and CD16/56+)
- Quantitative Ig:lg levels (including total Ig, IgG, IgG subtypes, IgM, and IgA)

Ocrelizumab—F. Hoffmann-La Roche Ltd
22/Statistical Analysis Plan BN29739

For each flow cytometry parameters, the absolute values and change from baseline (Day 1) will be summarized over time by treatment group. Summary statistics calculated will include mean, median, SD, minimum, and maximum. For CD19 cells, the number and percentage of patients whose CD19 counts have repleted will be presented at each timepoint. Repletion is defined as the CD19-cell count having returned to their baseline value (Day 1) or lower limit of normal (≥ 80 cells/ μL), whichever is lowest. The median CD19-cell count will be displayed graphically over time from the start of study treatment.

For immunoglobulin levels (IgG, IgM, and total Ig), the absolute values and change from baseline will be summarized over time by treatment group. Summary statistics calculated will include mean, median, SD, minimum, and maximum. At each timepoint, the number and percentage of patients with immunoglobulin levels lower than the lower limit of normal will be presented. For each immunoglobulin, the number and percentage of patients with single and replicated laboratory abnormalities will be summarized by treatment group. The mean immunoglobulin levels (IgG, IgM, and total Ig) will be displayed graphically over time from the start of study treatment.

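### Group B's extension-period laboratory and flow cytometry changes are measured from Day 1, about 12 weeks before its first ocrelizumab dose, whereas Group A's start at its first dose

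*SAP*

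**What the plan says.** SAP 4.6.4.1 opens by fixing its scope: "The summaries described below for general laboratory assessments will be produced for both the ISP and for the OOE separately". It then gives a single baseline rule with no variant for the OOE. For Group A, "The baseline value will be the last value prior to the first dose of ocrelizumab for patients in Group A"; for Group B, the last value "prior to the first immunization for patients in Group B". The same section provides for change from baseline in the safety follow-up after the OOE, if there are enough data, and again names no other baseline.

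SAP 4.5 produces separate immunophenotyping summaries for the ISP, the OOE and the follow-up periods. For flow cytometry, "the absolute values and change from baseline (Day 1) will be summarized over time by treatment group". The immunoglobulin paragraph that follows speaks of change from baseline without saying which day is meant.

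The two groups start ocrelizumab at different times. Protocol 3.1 says "Group A: Immunization Study Period and OCR treatment starts at Day 1/Week 1". For Group B it says "At Day 1/Week 1, patients will start to receive immunizations and undergo post-immunization assessments", and places the first ocrelizumab infusion at Day 84/Week 12, as the start of the OOE.

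**The concern.** The Group B rule suits the ISP, where Group B receives vaccines only. Carried into the OOE, it means that change from baseline describes different things in the two groups. In Group A it is change since ocrelizumab began. In Group B it is change since the first vaccine visit, with about 12 weeks off ocrelizumab included.

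Protocol 5.1.1.3 and 5.1.2.4 list decreased immunoglobulins and neutropenia among the ocrelizumab risks. The natural reading of an OOE change table is change on drug, and for Group B the plan does not produce it. SAP 4.6.4.1 also drops the listing of individual laboratory values, so the planned laboratory listings do not allow a reader to rebuild each patient's change.

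**Working it through.** The plan states no figure for this point, so the check is one of timing.

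**Inputs**
- Group A: baseline just before the Day 1 infusion; first ocrelizumab on Day 1; Dose 2 on Day 169 (SAP 4.6.4.1; Protocol 3.1).
- Group B: baseline just before the Day 1 vaccines; first ocrelizumab on Day 84; later OOE visits on Days 98, 238 and 252, with Dose 2 on Day 252 (SAP 4.6.4.1; Protocol 3.1; Protocol Appendix 1, Table B).

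**Gap from baseline to first ocrelizumab** = day of first infusion − day of baseline.
- Group A: 1 − 1 = 0 days.
- Group B: 84 − 1 = 83 days. With Table B's ±4-day window this is 79 to 87 days. It is longer when influenza vaccine is given after Week 12, because Protocol 4.4.2.5 then requires the infusion to be delayed.

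**Visits counted from each baseline**

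| Group, visit | Days since first ocrelizumab | Days since SAP baseline | Days since last pre-ocrelizumab value |
|---|---|---|---|
| A, Day 169 (Dose 2) | 168 | 168 | 168 |
| B, Day 98 | 14 | 97 | 14 |
| B, Day 238 | 154 | 237 | 154 |
| B, Day 252 (Dose 2) | 168 | 251 | 168 |

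At the Dose 2 visit both groups are 168 days from first ocrelizumab, but the SAP baseline puts Group B at 251 days. The pre-ocrelizumab anchor brings both to 168.

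**Does the sample exist?** Table B marks routine safety laboratory tests, flow cytometry and total Ig, IgA, IgG and IgM at Day 84. Footnotes 22 and 23 require flow cytometry and safety samples at infusion visits to be drawn before methylprednisolone, which itself precedes ocrelizumab. Footnotes 23 and 27 word this as applying to all blood samples at such visits. No new sample is needed.

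**CD19 repletion.** SAP 4.5 defines the threshold as the lower of the baseline count and 80 cells/µL, that is min(baseline, 80). Moving the baseline from Day 1 to Day 84 changes a patient's threshold only if min(Day 1, 80) differs from min(Day 84, 80), which requires at least one of the two counts to be below 80.

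**Number affected.** About 100 patients at 2:1 gives 100 × 1/3 ≈ 33 in Group B. All who enter the OOE are affected.

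**The case against.** The strongest reply is that both baselines are the last value before the first study intervention, nominally Day 1 in each group. SAP 4.6.2.1 counts vaccines as study treatment, and Protocol 6.5.2 itself refers to laboratory change from Day 1. On that view the rule is consistent and simply answers a different question. This stands as a reason to keep the Day 1 change. It does not supply the change since ocrelizumab began, which Group A's OOE columns show and Group B's do not.

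A reader might infer that the Day 1 baseline mixes vaccine and interferon effects into Group B's figures alone, and that re-anchoring would clear them. The documents do not support this:
- Group A receives TT, 23-PPV, three KLH doses and either 13-PCV or influenza vaccine at Weeks 12–20, after its own baseline and before its OOE starts. Its OOE change spans a vaccine course too. After re-anchoring, Group A's change would still include that course while Group B's would largely exclude it.
- Group B may stay on interferon until ocrelizumab starts, so interferon can be present at Day 1 and at Day 84 alike. Any effect of stopping it falls within the OOE change under either baseline.

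It is also fair to say that absolute values are tabulated by visit, so drift in the group average between Day 1 and Day 84 would be visible. If the same patients contributed at both times, mean change since Day 84 could be found by subtraction. The median, SD, minimum and maximum of within-patient change could not.

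Finally, no hypothesis is tested, OOE data at this cutoff are only what has accrued, and the groups enter the OOE at different doses (Dose 2 in Group A, Dose 1 in Group B). All of this limits the consequence.

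**Conclusion.** The point holds for general laboratory tests and flow cytometry. Group B's OOE change starts 83 scheduled days before its first ocrelizumab dose and Group A's starts 0 days before. Group B's tables therefore do not report within-patient change since starting ocrelizumab, and the two groups' columns are not aligned on time since first dose. This assumes the SAP baseline is applied to the OOE as written; the SAP gives no other.

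The consequence is limited to the reading of descriptive tables for up to about 33 patients. The primary endpoint is untouched, and the documents give no data from which to estimate the numerical shift.

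Three wider inferences should not be drawn:
- CD19 repletion is not generally misclassified. It changes only for patients with a Day 1 or Day 84 count below 80 cells/µL, and nothing in the documents suggests that is common in Group B before ocrelizumab.
- The SAP does not fix Day 1 as the immunoglobulin baseline in section 4.5. There the gap is that the baseline is unstated.
- Vital signs at infusion visits are not affected, because SAP 4.6.5 takes the pre-infusion value of that visit.

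**What to change.** Add one sentence to SAP 4.6.4.1 and one to SAP 4.5: for OOE and post-OOE summaries, Group B's change is presented from the last value before its first ocrelizumab infusion. Group A's rule already has this form. In SAP 4.5, also state the immunoglobulin baseline explicitly, and then apply the same rule to it.

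Keep the Day 1, pre-immunization baseline for Group B's ISP tables and for the change from Day 1 named in Protocol 6.5.2. A table footnote should say that the re-anchored columns are aligned on time since first ocrelizumab but not on vaccine exposure or interferon use.

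Defining the anchor as the last value before first ocrelizumab, and not as Day 84, also covers patients whose first infusion is delayed. The cost is a small amount of extra tabulation. No new sample or visit is required.
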